## PROMIS Integration Phase II (HUM00149448)

### Patient-Reported Outcomes Measurement Information System (PROMIS) Integration into Rheumatology Clinical Practice

#### Pilot Trial

##### 1.0. Background

Chronic medical conditions, such as rheumatic diseases (RD), have a detrimental effect on self-reported physical, mental, and social health, i.e., health-related quality of life (HRQOL) [1, 2]. RDs are diverse with variable impact on HRQOL, can fluctuate over time, and may mirror disease flares [3-5]. A patient-reported outcome (PRO) is any report of the status of a patient's health condition that comes directly from the patient, without interpretation of the patient's response by a clinician or anyone else [6]. PROs can supplement clinical decision making by aiding assessment and management of these conditions. There is increased enthusiasm within the rheumatology research community to integrate PRO measures with clinical assessments [7-9].

The National Institutes of Health Patient-Reported Outcomes Measurement Information System (PROMIS®) Roadmap initiative (available at <http://www.nihpromis.org>) is a cooperative research program designed to develop, evaluate, and standardize item banks to measure PROs across patients with varying medical conditions and in a cross section of the US population [10]. PROMIS® aims to use item response theory (IRT) to develop reliable and valid item banks that can be administered as short forms and computerized adaptive tests (CAT) [11, 12]. As it improves measurement precision, it lessens burden on the patient. PROMIS short forms are available for incorporation in the electronic medical records [13].

The overarching aim of our project is to lay the groundwork for a well powered randomized controlled trial to assess the impact of incorporating PROs – specifically PROMIS questionnaires – at the point of care in clinical rheumatology practice. This IRB application is for a pilot study to assess the feasibility of a future randomized controlled trial (RCT) of strategies to promote review and discussion of PROs during rheumatology consultations. The current pilot trial will yield important preliminary results to help us design a future RCT, including assessment of the following:

- Recruitment and retention
- Data collection procedures
- Required resources and management capacity
- Intervention acceptability and feasibility
- Expected intervention effect and variability
- Provide data to assess sample size for definitive trial

We will also qualitatively assess health care provider (HCP) and patient perspectives on the barriers and facilitators of integrating PRO use into rheumatology care

## PROMIS Integration Phase II (HUM00149448)

### 2.0. Preliminary Work

There are a number of requirements of integrating PRO assessment into a clinical practice to make it feasible and easily acceptable amongst providers – (a) PRO data should be collected completely and accurately with little effort, (b) the scoring of the data should be automated and happen in real time during the clinic visit, (c) the PRO data should be longitudinally stored in patient's electronic medical record and should be easily retrievable to allow monitoring, and (d) the scores should be represented in a format that is easy to understand for both the provider and patient [14-16].

We conducted a multi-phase study at MM titled Patient Reported Outcomes Measurement Information System (PROMIS) in Rheumatology - HUM00076269. In this study, we iteratively collected data to 1) identify the PROMIS health domains most relevant to the care of patients with RDs; 2) identify clinically meaningful cut-points for PROMIS domains with input from patients and HCPs using real patient data collected at MM, and 3) incorporate PROMIS domains in the MM EMR.

#### Completed Preliminary Work Phase 1: Consensus from rheumatology care providers

We conducted focus group discussions with practicing rheumatologists at MM to identify PROMIS domains that are clinically relevant and actionable at the point of care. They identified four domains—physical function, pain interference, sleep disturbance, and depression—as important in patients with rheumatic diseases and actionable in clinical practice [7]. There was also consensus among HCPs to incorporate PROMIS domains in the EMR along with guidance where appropriate action needs consideration.

#### Completed Preliminary Work Phase 2: Identify clinically meaningful cut-points for chosen domains

Initially, data on T-scores across different domains - physical function, pain interference, sleep disturbance, and depression – were collected in a convenience sample of patients with RDs at MM. Subjects were enrolled, and data was collected using the Assessment Center® (a free, online data collection tool that enables researchers to create study-specific websites for capturing PROMIS). The scores in PROMIS measures are computed to a T-score metric, where 50 represents the mean for US general population, and 10 is the standard deviation. A higher PROMIS T-score represents more of the concept being measured (except physical function where a lower T-score indicates increased impairment). The team adapted the bookmark standard-setting procedure for creating clinical vignettes at different cut-points. This method is routinely used in educational and psychological testing and was recently used to develop vignettes in multiple sclerosis, juvenile inflammatory arthritis, and in oncology settings [17-19].

Nine patients and 10 HCPs participated in a 2-day expert panel meeting at MM. Eight of the nine patients were women. There was large variability in patients classified as having severe impairment in physical function (24% by patients and 2% by HCPs).

## PROMIS Integration Phase II (HUM00149448)

**Table 1: Clinically Meaningful Scores for Different Severity of Physical Function**

Clinically Meaningful Scores for Different Severity of Physical Function				
Clinical vignettes Category	Cut scores*		Severity level when applied to UM cohort (N=233)	
	Patient classification	HCP classification	Patient classification	HCP classification
			%	%
No problem	>65	>60	0.4	1
Mild problem	45-65	45-60	27	26
Moderate problem	35-45	25-45	48	70
Severe problem	<35	<25	24	2

**\*Mean for US population is 50 with higher score is better physical function**

Table 1 shows cut points reached separately by patients and HCPs for the physical function domain. In the patient classification, across physical function domains, the categories tended to have a T-score distribution that was within 0.5-1 SD of HCPs, except for moderate and severe problems where the difference was 1 SD. Based on these, a majority of the patients [75-96%] would be classified as having none to mild to moderate problems with physical function.

### Completed Preliminary Work Phase 3: Incorporate PROMIS short forms in MM EMR

The PROMIS item banks for physical function, pain intensity, and sleep disturbance have now been integrated into MiChart (EPIC EMR at MM). The PROMIS data is collected in selected MM rheumatology clinic locations and by selected HCPs as part of standard of care. The PROMIS questionnaires are completed by patients either via online portal or on tablet at check-in before the clinic appointment with the HCP. Currently, two rheumatology clinic locations are equipped with portable tablets for collecting PROMIS questionnaire data. Rheumatology HCPs currently participate in this set-up where in, all their patients are given these tablets to complete the questionnaire while in the waiting room. The scores from these PROMIS questionnaires are available for display in two formats (Figures 1-2) on MiChart (electronic medical record used at MM). The box labeled 'PROMIS score interpretation' denotes the interpretation of the physical function score and also provides an actionable cut point (chosen as 30 [Table 1]—the average between patients' and HCPs' cut-scores for severe physical limitations in Table 1) and recommendations. While the tabular format (Figure 1) is importable into the encounter note, the graphical format is not importable. HCPs can generate the graphical format with numerical scores (Figure 2) for discussions with the patients during the encounter. Figure 2 shows incorporation of the PROMIS item bank (physical function and pain intensity are shown as examples) in the MM EMR. Also, HCPs can track changes in PROMIS scores over time (red arrow). The pre-visit PROMIS questionnaires are administered as standard of care to patients across all MM Rheumatology clinics.

### PROMIS Score interpretation

Domain	Interpretation
Pain Intensity	A higher score denotes more pain intensity. A score of greater than or equal to 5 is suggestive of moderate-to-severe pain. Consider evaluating the cause(s) of the ongoing pain and management of pain (including pharmacologic and non-pharmacologic management and appropriate referral).
Physical Function	The mean score for the US general population is 50. A higher score denotes a better physical function. A score of less than or equal to 40 is suggestive of moderate-to-severe limitation in physical function. Consider optimizing therapy (such as PT or change in medication) or reevaluation at follow up visit.
Sleep disturbance	The mean score for the US general population is 50. A higher score denotes worse sleep disturbance. A score of greater than or equal to 60 is suggestive of moderate-to-severe impact in their sleep quality. Consider optimizing therapy (such as referral to sleep medicine), counseling about sleep hygiene, or reevaluation at follow up visit.)

## PROMIS Integration Phase II (HUM00149448)

**Figure 2: Screenshot of PROMIS physical function, pain intensity, and sleep disturbance on MiChart**

### 2.1. Phase I (HUM00145286)

**Part A:** The feasibility of administering the PROMIS questionnaire to patients using a tablet in multi-HCP rheumatology clinics at Michigan Medicine was assessed between July 1, 2016 and March 31, 2018 [20]. Of all patients seen in clinic, 87.2% completed the PROMIS® questionnaires, of which 82.4% used tablets at check-in, 14.1% completed at home (portal), and 3.4% were assisted on a clinic desktop computer to complete the questionnaire. Around 13% of patients did not complete questionnaires due to various reasons – lack of portal access, limited tablet availability at check-in, time constraints for MAs in a busy clinic, and rarely, patient refusal to complete.

**Part B:** Seven rheumatology HCPs were invited to participate in a study from January 2019-January 2020 to assess the feasibility and impact of training on use of the PROMIS scores. Participating HCPs were educated in a session on how to import the PROMIS scores into the encounter note. Of 5041 clinical encounters reviewed, patients had not completed PROMIS® questionnaires in 1072 (21%) of the encounters. Of the remaining 3969 encounters, PROMIS® scores were imported to the note in 2745 encounters (69.2%). In these encounters, providers had documented their interpretation of the PROMIS® scores in 2261 (82.3%) notes. In feedback sessions over the course of the year, HCPs shared challenges they encountered with using PROs in practice. The most frequent reason for not importing the scores to the note was a new workflow pattern for the providers to remember during their office encounters. Another less common reason for not importing PRO scores into the note was the presence of a trainee participating in the visit and doing the initial documentation. Overall, the providers felt it was easy to import the scores using the dot phrase and to complete the subsequent documentation.

## PROMIS Integration Phase II (HUM00149448)

### 3.0. The Proposed Study: PROMIS Integration into Clinical Rheumatology Practice (Pilot trial)

#### 3.1. Specific Aims

The goals identified for this study are centered on appraising HCP documentation and referrals as well as patient-provider communication.

Aim 1: To assess the HCP documentation of PROs in the electronic medical record (EMR) as a result of PROMIS report card availability at the point-of-care.

Aim 2: To determine the presence or absence of appropriate HCP referrals in the electronic medical record (EMR) as a result of PROMIS report card availability at point-of-care.

Aim 3: To evaluate the patient-provider communication due to PROMIS score availability at point-of-care.

#### 3.2. Hypotheses

Providing PROMIS scores to patients and HCPs at point-of-care will give both patients and HCPs an objective tool to track symptoms' progression over time. Patients will be empowered to discuss symptoms and issues of concern with their HCPs, and can be actively involved in decisions about medications and other treatments. We hypothesize that, compared to not, providing PROMIS scores to patients and HCPs at the point-of-care will be associated with:

1. Improved documentation of PRO scores in the EMR (primary outcome)
2. Incorporation of the interpreted data in medical decision-making about treatments or referrals (secondary outcome)
3. Improved patient-provider communication (secondary outcome)
4. Improved PROMIS symptoms (secondary outcome)
5. Improvements in health outcomes as measured by PROs (exploratory)
6. Improved patient satisfaction with treatment (exploratory outcome)
7. Improved patient satisfaction with care (exploratory outcome)

A comprehensive integration of PROs into clinical care involves not only patients, but also HCPs, and may be even more effective than providing PRO scores to patients alone. In addition, we will use qualitative research approaches to explore the effects of PRO implementation as well as patient and HCP expectations and doubts regarding PRO implementation.

## PROMIS Integration Phase II (HUM00149448)

**Table 2. Primary, Secondary, and Exploratory Endpoints**

Assessment	Description	Timeframe
PRIMARY ENDPOINTS		
Percent of appointments at which PROMIS scores are documented in the EMR note by the participating HCP	Documentation in EMR notes will be categorized as either 'yes' or 'no' and identified through EMR data pulls.	Each appointment with the HCP during the trial period
SECONDARY ENDPOINTS		
Percent of appointments at which referrals/recommendations related to PROMIS scores are documented in the EMR note by the participating HCP	Documentation in EMR notes will be either 'yes' or 'no' and identified through EMR data pulls.	Each appointment with the HCP during the trial period
Quality of patient-provider communication	Patient-reported assessment of different aspects of patient-provider communication using the Interpersonal Processes of Care (IPC) Survey (29 items), which measures 7 subscales: hurried communication, elicited concerns/responded, explained results/medications, patient-centered decision making, compassion, discrimination, and disrespectful office staff (score for each subscale ranges from 1-5; a higher score indicates better IPC) [24].	Up to 2 weeks after baseline appointment
Change in score of the most bothersome PROMIS domain from baseline to 3 months	Change in the T-score of the most bothersome PROMIS domain at baseline for sleep disturbance and physical function domains, and change in actual score on a scale 0-10 for pain intensity domain.	3 months post-baseline appointment
EXPLORATORY ENDPOINTS		
Percent of participants reporting discussion of PROs with their rheumatology provider during appointments	Patient report of whether or not PROs were discussed during appointment (assessed via survey).	Up to 2 weeks after baseline appointment

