**Figure 3. Study Flowchart**

## PROMIS Integration Phase II (HUM00149448)

**Figure 4. Study Schedule of Events**

	Screening*	Baseline/ enrollment**	3 months after baseline appointment	End of study
For patients:				
Informed consent	X			
Patient background survey	X			
PROMIS questionnaires *** (pain intensity, physical function, and sleep disturbance)	X		X	
Email with PRO scores to patients in Arm 1****		X		
Post-appointment survey		X		
3 month follow-up survey			X	
Patient interview (Optional)				X
For HCPs:				
Informed consent	X			
Email Arm 1 enrolled patient PRO score summaries to HCP1		X		
Post-study interview				X

\*Patients will be in the screening phase from time of consent to first reported concerning PROMIS score.

\*\*Patients are enrolled only after reporting a concerning PROMIS score.

\*\*\*Patients are asked to complete PROMIS questionnaires prior to visits as part of standard of care; only PROMIS scores from patients who opt in for screening will be reviewed for eligibility.

\*\*\*\*Only Arm 1 receives scores

Patients will have up to 2 weeks to complete surveys/questionnaires.

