### 3.6.2.4. Outcome Assessment

Health outcomes (PROMIS pain intensity, physical function and sleep disturbance) will be assessed before appointments and at three (3) months post appointment with an online patient-reported survey.

Patient-provider communication, the patient's experience with the PRO scores, and satisfaction with disease management will be assessed with a patient-reported survey after the appointment.

Process of care measures (documentation and interpretation of PRO scores, clinical decisions) will be assessed for each appointment using data from the EMR (notes, medication changes, and referrals). We will utilize the Data Direct tool to assist with exporting quantitative data from the EMR, and the EMERSE tool to assist with reviewing textual data from the EMR (<https://research.medicine.umich.edu/our-units/data-office-clinical-translational-research/data-access/self-serve-data-tools>).

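### Documentation and referrals are counted at every appointment with no per-patient window, report cards are scheduled only at baseline, and the planned intervals make no allowance for repeat visits

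*Combined protocol and SAP*

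**What the plan says.** The primary endpoint in Table 2 is "Percent of appointments at which PROMIS scores are documented in the EMR note by the participating HCP", with the timeframe "Each appointment with the HCP during the trial period". The referral endpoint has the same unit and timeframe. Section 3.6.2.4 agrees: process-of-care measures "will be assessed for each appointment using data from the EMR". By contrast, communication and satisfaction outcomes "will be assessed with a patient-reported survey after the appointment". Every other endpoint in Table 2 is tied to the baseline appointment, either up to 2 weeks or 3 months after it.

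The trial period is not defined for a patient. Section 3.3 gives one duration for the whole study: a minimum of 12 months, or until recruitment is adequate.

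Figure 4 has two rows for the Arm 1 intervention, "Email with PRO scores to patients in Arm 1" and "Email Arm 1 enrolled patient PRO score summaries to HCP". Both are marked under Baseline/enrollment and nowhere else, and the figure has no column for later appointments. Section 3.6.2.2 describes the emailed card without saying whether it is sent once or before each visit. Section 3.4 requires completed PROMIS measures before the baseline appointment only. Scores at later visits would come from routine care: "Patients are asked to complete PROMIS questionnaires prior to visits as part of standard of care" (Figure 4), and "The pre-visit PROMIS questionnaires are administered as standard of care to patients across all MM Rheumatology clinics" (section 2.0, Phase 3).

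For categorical outcomes, section 3.7.1 plans a count, a proportion and a 95% confidence interval. It gives no method for repeated visits. The reference list includes a comparison of GEE with mixed models, but the analysis section does not draw on it.

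**The concern.** Aim 1 asks what the report card does to documentation. As written, the endpoint pools the appointment that has a scheduled card with any later appointments, for which the plan does not say whether there is a card. Two separate problems can follow.

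- **Precision.** Several appointments from one patient are not independent. A binomial interval over appointments treats them as if they were, and is too narrow when visits within a patient are positively correlated.
- **What is estimated.** If later visits have no card, the pooled arm difference mixes the card's effect with visit frequency and carry-over. Because the only period given is study-level, patients enrolled early could also contribute more appointments than those enrolled late.

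Section 3.7.1 offers no power calculation and justifies the sample by the point estimates it will supply for a Phase 3 design. An estimate and interval that depend on an undefined window weaken what the pilot is meant to deliver.

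**Working it through.** **The plan's own figures.** The 300 patients are a convenience sample with no formula, so there is nothing to reproduce. The Phase I rates in section 2.1, Part B do reproduce: 1072/5041 = 21.3% of encounters had no questionnaire, and 2745/3969 = 69.2% of the rest had scores imported. Over all encounters the import rate is 2745/5041 = 54.5%, so how visits without scores are handled matters to a percent-of-appointments endpoint.

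**Inputs.** From section 3.7.1: up to 300 patients randomised 1:1, so 150 per arm. Assumed, because the documents give no value:

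- k, later visits per patient: 0, 1 or 2, equal for all
- ICC, within-patient correlation: 0.2 to 0.5
- g, share of later visits with a card: 0, 0.5 or 1
- c, share of the effect carried over to visits without a card: 0, 0.5 or 1
- both arm proportions at 50%, the widest case

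**Precision.** Plain half-width for the arm difference = 1.96 × √(2 × 0.25 / n), with n = 150(1 + k). Design effect DE = 1 + k × ICC. Correct half-width = plain × √DE. Actual coverage of the plain interval = 2Φ(1.96/√DE) − 1.

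| Visits per patient | n per arm | Plain, points | DE (ICC 0.2; 0.5) | Correct, points | Coverage of plain interval |
|---|---|---|---|---|---|
| 1 (k = 0) | 150 | ±11.3 | 1 | ±11.3 | 95% |
| 2 (k = 1) | 300 | ±8.0 | 1.2; 1.5 | ±8.8; ±9.8 | 92.6%; 89.0% |
| 3 (k = 2) | 450 | ±6.5 | 1.4; 2.0 | ±7.7; ±9.2 | 90.2%; 83.4% |

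The plan does not specify an interval for the arm difference. Coverage and the √DE ratio are the same for a single arm's proportion; the half-widths are not. The table leaves out correlation among patients of the same HCP.

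**Dilution.** Fraction of the index-visit effect seen after pooling: F = (1 + k[g + (1 − g)c]) / (1 + k).

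| g | k | c = 0 | c = 0.5 | c = 1 |
|---|---|---|---|---|
| 0 | 1 | 0.50 | 0.75 | 1.00 |
| 0 | 2 | 0.33 | 0.67 | 1.00 |
| 0.5 | 1 | 0.75 | 0.88 | 1.00 |
| 0.5 | 2 | 0.67 | 0.83 | 1.00 |

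With k = 0 or g = 1, F = 1.00.

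**Trade-off.** With k = 1, pooling multiplies the correct half-width by √(DE/2): √0.6 = 0.77 at ICC 0.2 and √0.75 = 0.87 at ICC 0.5. With g = 0, F = (1 + c)/2. Pooling therefore improves the ratio of effect to error only if c exceeds 2 × 0.775 − 1 = 0.55 (ICC 0.2) or 2 × 0.866 − 1 = 0.73 (ICC 0.5).

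**The case against.** The strongest reply is that dilution arises on only one of three readings. Patients may have a single counted appointment: Figure 4 schedules no later one, and much of the text speaks of the appointment in the singular. Or a card may precede every counted visit: section 3.6.2.2 does not restrict it to baseline, and section 3.3 keeps the intervention active throughout. On either reading nothing is diluted. This stands. A reader might infer that the Aim 1 estimate is diluted as designed, and the documents do not establish that. They leave card timing unresolved and set no window, so dilution is conditional.

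Two other inferences go too far. One is that the unit of analysis is unclear. Table 2 states it as a percentage of appointments, and the singular wording in section 3.6.2.4 concerns the patient survey, a different outcome. The other is that Fisher's exact test is the planned test for this endpoint. In section 3.7.1 that sentence directly follows the comparison of baseline characteristics and may apply only there.

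It can also be said that counting every visit under an assigned strategy is a legitimate estimand, that the 21% without scores may overstate the gap (Part A of Phase I found about 13%, and trial patients need portal access and receive reminders), and that this is a pilot with no power claim. All three are fair. They argue for keeping all visits if that is the intention, but they supply neither the window, nor the card rule, nor a method for repeat visits.

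**Conclusion.** The concern holds in conditional form and should be fixed before the EMR data are analysed. The open-ended per-appointment count, the baseline-only marking of the emails and the lack of any repeated-visit method are all in the text.

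- If patients have more than one counted appointment and their visits are positively correlated, the plain 95% interval under-covers whether or not cards are repeated: about 93% to 89% with two visits and 90% to 83% with three, for ICC 0.2 to 0.5.
- If later visits also lack a card, the arm difference is diluted unless carry-over is complete, to as little as half the index-visit effect with one later visit and no carry-over.

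These sizes rest on assumed visit counts, correlation and carry-over. With one appointment per patient, neither within-patient problem arises. A reader might then conclude that the interval is sound, but that does not follow. Documentation is an HCP behaviour, and one HCP may see many trial patients, so observations can still be correlated within HCP. Because patients are randomised individually, one HCP may have patients in both arms, which may limit the harm to the arm difference.

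**What to change.** 1. Reconcile Table 2, Figure 4 and sections 3.6.2.2 and 3.6.2.4 on whether a card precedes every counted appointment. State a per-patient window and a rule for appointments with no PROMIS scores.
2. If cards are sent at baseline only, define the primary and referral endpoints as yes/no at the index appointment, one observation per randomised patient. Section 3.4 already ensures that scores exist there. Report later appointments separately as persistence, using GEE or a mixed model clustered on patient.
3. If cards precede every counted appointment, keep all appointments and use the patient-clustered analysis for the primary comparison.
4. In either case account for HCP, for example as a stratum or a random effect, and name the estimator and interval for the arm difference in section 3.7.1.

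**Cost.** An amendment to Table 2 with matching edits to the sections above and to section 3.7.1. The EMR pull is the same and no new data are collected. Under option 2, follow-up visits leave the primary endpoint and the interval widens to about ±11.3 points, against ±8.8 to ±9.8 for a correctly clustered analysis with one later visit, under the assumptions above.

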#### 3.6.2.2. Interventions

##### **PRO Integration into Clinical Practice Treatment Group**

For Arm 1, PRO scores will be shared with patients and HCPs via an emailed report card in order to facilitate discussion of the PRO scores during consultation. HCPs will document their discussion and recommendations/referrals using the dot phrase in MiChart (Epic EMR).

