##### **Usual Care Control Group**

For Arm 2, patients and HCPs will not receive an emailed PROMIS score report. PROMIS scores, however, will be available in the EMR as usual. This arm will receive *usual care*.

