## PROMIS Integration Phase II (HUM00149448)

- Patient will be asked to complete a single-item survey to rank the PRO domains in order of importance.
- Depending on what domain patients indicate is the most concerning to them, patients will be placed into one of 3 groups: "Concerning pain", "Concerning sleep", or "Concerning physical function".

A permuted block randomization scheme stratified by most concerning PRO domain (pain, sleep, physical function) will be created before enrollment begins. Once a participant has completed the screening and evaluation for inclusion/exclusion criteria, the participant will enter the randomization process. Participants will be randomized to Arm 1 and Arm 2 with equal probability (1:1) in RedCap. At time of randomization, the investigator or study coordinator will use the randomization sheet to obtain the assigned randomization number and intervention assignment. In this study, participants and physicians will know the assigned treatment group.

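### The Table 2 referral endpoint is read from notes whose documentation is prescribed only in Arm 1, so on its own it cannot show whether referrals increased (Aim 2)

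*Combined protocol and SAP*

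**What the plan says.** Aim 2 (Section 3.1) reads: "To determine the presence or absence of appropriate HCP referrals in the electronic medical record (EMR) as a result of PROMIS report card availability". Hypothesis 2 (Section 3.2) asks something different: "Incorporation of the interpreted data in medical decision-making about treatments or referrals (secondary outcome". The Table 2 row that has to serve both is "Percent of appointments at which referrals/recommendations related to PROMIS scores are documented in the EMR note by the participating HCP". It is scored yes or no at each appointment from EMR data pulls. Table 2 gives no rule for when an action is related to the scores, and it neither defines nor assesses appropriateness.

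The description of note-writing differs by arm. For Arm 1, Section 3.6.2.2 states: "HCPs will document their discussion and recommendations/referrals using the dot phrase in MiChart (Epic EMR". The Arm 2 text has no such sentence. It withholds the emailed report and adds: "PROMIS scores, however, will be available in the EMR as usual". On masking, Section 3.6.2.3 states: "In this study, participants and physicians will know the assigned treatment group".

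Section 3.6.2.4 says that process-of-care measures "will be assessed for each appointment using data from the EMR (notes, medication changes, and referrals". Table 3, whose measures are to be compared between arms, lists a Clinical decision variable (medication change, referral or no action among the categories). It carries no condition that PROMIS be mentioned, but it is not a Table 2 endpoint.

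**The concern.** The intervention, as described, includes a way of writing the very text from which the endpoint is scored. If Arm 1 notes record and label referrals more fully, the row rises in Arm 1 even when clinicians refer equally often in both arms.

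This matters because it is the only Table 2 endpoint on clinician referrals or actions. Section 3.7.1 says that the pilot should give point estimates robust enough to design a Phase 3 trial, and that the next trial will test the effect on decision making, among other outcomes. A documentation difference could be carried forward into that design as a referral effect.

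**Working it through.** **1. What each item counts**

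| Item | What is counted | Read from | Tied to PROMIS? | Table 2 endpoint? |
|---|---|---|---|---|
| Aim 2 (3.1) | Appropriate referrals, present or absent | EMR | Attributed to the report card; no labelling required | – |
| Hypothesis 2 (3.2) | Use of interpreted scores in decisions | Not stated | Yes, by its nature | – |
| Table 2 referral row | Referrals and recommendations | HCP's note | Yes | Yes, secondary |
| Table 3 Clinical decision | Medication change, referral, no action | EMR (3.6.2.4) | No | No |

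The Table 2 row matches hypothesis 2. Against Aim 2, it adds two conditions (in the note, and related to the scores), adds recommendations, and leaves out appropriateness.

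**2. One referral, two arms**

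In Phase I (Section 2.1, Part B) the dot phrase is the means of bringing scores into the note: "Overall, the providers felt it was easy to import the scores using the dot phrase and to complete the subsequent documentation". Suppose that Section 3.6.2.2 means the same tool, which is an inference. Take one sleep-medicine referral for a patient with a concerning sleep score, ordered identically in either arm.

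- If *related* is judged from PROMIS wording, the referral counts in Arm 1 when the dot phrase is used and may not count in Arm 2.
- If *related* is judged by domain, as the actions in the PROMIS Score interpretation table would allow, PROMIS wording is not needed. The row is still read from the note, however, and only Arm 1 has a described way of recording referrals there. An order without matching note text is missed, possibly more often in Arm 2.

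The plan does not choose between these readings.

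**3. Illustration of size**

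There is no plan figure to reproduce: no rate, effect size or power is given for this row, and the 300 patients are a convenience sample.

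Let r be the true referral rate per appointment, equal in both arms. Let L1 and L2 be the shares of referrals that the row captures as related in Arms 1 and 2.

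- Observed rates: p1 = r × L1 and p2 = r × L2
- Spurious difference: r × (L1 − L2)
- 95% half-width: 1.96 × √[p1(1 − p1)/150 + p2(1 − p2)/150], taking 300/2 = 150 per arm, one appointment per patient and no clustering by HCP

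Phase I supplies stand-ins for L2. Completed encounters were 5041 − 1072 = 3969. Scores were imported in 2745/3969 = 69.2%, and imported and interpreted in 2261/3969 = 57.0%. These are rates over all completed encounters, not labelling rates among referrals. The values of r and L1 are assumptions.

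| L1 vs L2 | Observed at r = 40% | Difference (95% CI), points | r = 20% | r = 60% |
|---|---|---|---|---|
| Equal | Equal | 0 | 0 | 0 |
| 80% vs 69.2% | 32.0% vs 27.7% | 4.3 (−6.0 to 14.7) | 2.2 | 6.5 |
| 90% vs 57.0% | 36.0% vs 22.8% | 13.2 (3.0 to 23.4) | 6.6 | 19.8 |

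If carry-over between arms halves the labelling gap, the two differences at r = 40% fall to 2.2 and 6.6 points.

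**4. Why the row alone cannot settle it**

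The result 36.0% vs 22.8% arises with a true rate of 40% in both arms and labelling of 90% vs 57.0%. It arises equally with labelling of 57.0% in both arms and true rates of 0.36/0.57 = 63% in Arm 1 and 40% in Arm 2. The row identifies only the product r × L, whatever values are chosen.

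**The case against.** The strongest reply is that the plan already holds most of what is needed. Clinical decision in Table 3 is to be compared between arms with no PROMIS condition, and Table 3 lists documentation and interpretation separately. A reader might infer that the trial has no measure of referrals free of PROMIS wording; the documents do not support that. What stands is narrower: the variable is outside Table 2, is not linked to Aim 2, and is not tied to the patient's concerning domain.

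A reader might also take this row to be the only Table 2 endpoint on decisions. It is not: the Interpersonal Processes of Care row includes a patient-reported decision-making subscale. That subscale does not measure referrals.

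Second, Aim 2 speaks of referrals resulting from report card availability, so a relatedness condition is one way to make it operational. That is fair as a reading. In a randomized comparison, though, attribution can come from the contrast between arms and needs no label in the note.

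Third, the difference between arms may be small. Arm 2 clinicians can see the scores and are not barred from the dot phrase. Patients, not clinicians, are randomized, so one HCP may see both arms. Trained HCPs in Phase I imported scores in 69.2% of completed encounters. All of this could narrow the gap, but none of it decides how the row is to be scored.

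Finally, deciding from notes whether a medication change addresses a domain would let the documentation difference back in. That is correct, and it shapes the fix.

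**Conclusion.** The concern holds as a limit on interpretation. A between-arm difference on the Table 2 referral row can reflect documentation or labelling rather than more referrals, so the row alone does not answer Aim 2. It remains a reasonable process measure for hypothesis 2.

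A reader might go further and conclude that the endpoint is biased by a known amount, or that any Arm 1 advantage will be spurious. The documents do not support this. They give no referral or labelling rates, the identity of the dot phrase is inferred from Phase I, and equal labelling gives no bias. The 4.3 and 13.2 points show what assumed labelling gaps would produce at an assumed 40% rate; they are not estimates for this trial.

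The point affects a secondary endpoint in a pilot. It is worth correcting because that endpoint may inform the next trial and the data for a cleaner measure are already planned.

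**What to change.** - **Aim 2.** Add to Table 2 a secondary endpoint: any referral order at the baseline appointment, taken from EMR orders whether or not PROMIS is mentioned. Classify it from the order itself against a list written in advance by concerning domain, applied identically in both arms. The actions in the PROMIS Score interpretation table can be the starting list. The list also gives *appropriate* a working definition.
- **Several concerning domains.** Use the domain that set the patient's randomization stratum (Section 3.6.2.3).
- **Medication changes.** Report them as a separate component through Table 3 Clinical decision, without judging relatedness from note text.
- **Hypothesis 2.** Keep the present row as a process measure, and state how *related* is judged.
- **Contrast.** State that Arm 1 differs from Arm 2 by the report card plus the documentation instruction.

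Neither arm, the sample size nor the planned EMR sources change. The cost is somewhat more record review and some judgement in building the list. Advice recorded only as note text, such as counselling, is left out of the Aim 2 endpoint.
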